Participants must be followed for at least 100 days after the last dose of study therapy. Follow-up visit 1 (FU1) occurs approximately 35 days (+/- 7 days) after last dose of coinciding with the date of discontinuation (+/- 7 days) if the date of discontinuation is greater than 35 days after the last dose. Follow-up visit 2 (FU2) occurs approximately 80 days (+/- 7 days) after FU1. Survival visits are every 3 months from FU2 up to 5 years and may be conducted during a clinic visit or via the phone. The primary endpoint of this study is PFS with a secondary endpoint of OS so tracking reporting the participant's status in the follow-up setting according to the protocol guidelines for disease progression and survival are critical to the final study analysis. The importance of follow-up should be clearly communicated to study participants. If the study drug(s) is discontinued prior to

the patient completion of the study, the reason for the discontinuation must be documented in the patient's medical records and entered on the appropriate case report form (CRF) page.

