Adverse Events Assessment	X	X	NSAEs and SAEs must be collected up to 30 days after study drug discontinuation. SAEs that relate to any later protocol specified procedure must be collected. SAEs should be reported through the MCRN protocol outlined in Section 8.1.
Review of Concomitant Medications	X	X	
Extended Laboratory Tests	X		CBC with differential, uric acid, BUN or serum urea level, creatinine, Na, K, Ca, Mg, phosphorus, chloride, bicarbonate (optional), amylase, lipase, glucose, AST, ALT, total bilirubin, alkaline phosphatase, LDH.
Thyroid Function Testing	X		TSH (reflex to free T3 and free T4 if abnormal result).
Pregnancy Test	X		Serum or urine.

Efficacy Assessments			
Radiographic Tumor Assessment	See Note	See Note	See Table 7.4-1 and Table 7.4-2 for CT and MRI scan schedule.
Exploratory Biomarker Testing			
Serum, Whole Blood, Tumor Biopsy	See Note		See Table 7.5-1 for biomarker sampling schedule.
Participant Status			
Survival Status	X	X	Every 3 months after follow-up visit 2; may be accomplished by visit or phone contact, to update survival information and assess subsequent anti-cancer therapy.

A-Follow-up visits occur as follows: X01 = 35 days  $\pm$  7 days from last dose, X02 = 80 days  $\pm$  7 days from X01

B-Survival visits continue every 3 months  $\pm$  14 days after Follow-up Visit 2 until death, lost to follow-up, or withdrawal of study consent

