### **8.1.1 Serious Adverse Event Collection and Reporting**

The Investigator Brochure (IB) contains Reference Safety Information to determine expectedness of serious adverse events for expedited reporting. Following the participant's written consent to participate in the study, all SAEs, whether related or not related to the study, must be collected, including those thought to be associated with protocol-specified procedures.

All SAEs must be collected that occur during the screening period and within 100 days of discontinuation of dosing. If applicable, SAEs must be collected that relate to any later protocol-specified procedure. The investigator must report any SAE that occurs after these time periods and that is believed to be related to the

study or protocol-specified procedure. An SAE report must be completed for any event where doubt exists regarding its seriousness. All SAEs must be reported to BMS Worldwide Safety. The BMS SAE form should be used to report SAEs.

If the investigator believes that an SAE is not related to the study, but is potentially related to the conditions of the study (such as withdrawal of previous therapy or a complication of a study procedure), the relationship must be specified in the narrative section of the SAE Report Form.

SAEs, whether related or not related to study drug, and pregnancies must be reported to BMS (as below) and to the study sponsor, Moffitt Cancer Center, through the MCRN coordinating center within 24 hours of awareness of the event. SAEs must be recorded on the SAE Report Form; pregnancies on a Pregnancy Surveillance Form (electronic or paper forms).

To ensure patient safety, each serious adverse event must be reported to the BMS, the PI and to the MCRN coordinating center within 24 hours of the investigational staff's knowledge. All participating sites will report SAEs by completing an SAE report in OnCore, the electronic data capture system. The SAE must be reported by email ([[contact]](mailto:[contact])) to the MCRN within 24 hours of discovery.

The preferred method for SAE data reporting collection is through the eCRF. The paper SAE/pregnancy surveillance forms are only intended as a back-up option when the eCRF system is not functioning. In this case, the paper forms are to be transmitted via email or confirmed facsimile (fax) transmission to both :

**SAE Email Addresses:** [[contact]](mailto:[contact]) , [[contact]](mailto:[contact])

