### 8.2.1 Nonserious Adverse Event Collection and Reporting

NCI CTCAE Version 4.0 will be utilized for grading of all nonserious adverse events.

The collection of nonserious AE information should begin at initiation of the study. Data will be captured in OnCore, Moffitt's Clinical Trials Database. To obtain access to OnCore, the site research staff must complete forms provided by the MCRN Regulatory Coordinator. Once the completed forms are received, the site coordinator will receive DUO access, logon/password, and information on how to access OnCore. The MCRN Coordinating Center will provide OnCore training to the site once initial access is granted and on an ongoing basis, as needed.

Nonserious AEs should be followed to resolution or stabilization, or reported as SAEs if they become serious (see Section 8.1.1). Follow-up is also required for nonserious AEs that cause interruption or discontinuation of study drug and for those present at the end of study treatment as appropriate. All identified nonserious AEs must be recorded and described on the nonserious AE page of the OnCore CRF. All nonserious AEs (not only those deemed to be treatment-related) should be collected continuously during the treatment period and for a minimum of 100 days following the last dose of study treatment. Completion of supplemental CRFs may be requested for AEs and/or laboratory abnormalities that are reported/identified during the course of the study.

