### **9.5.3 Safety Analyses**

Safety analyses will be performed for all treated participants. Descriptive statistics of safety will be presented using National Cancer Institute (NCI) Common Terminology Criteria for Adverse Events (CTCAE) version 4.0. All on-study AEs, drug-related AEs, SAEs and drug-related SAEs will be tabulated using worst grade per NCI CTCAE v4.0 criteria by system organ class and MedDRA preferred term. The listings by participant will be produced for all deaths, all SAEs, and all AEs leading to discontinuation of study drug. On-study laboratory parameters including hematology, chemistry, liver function, thyroid function, and renal function will be summarized using worst grade per NCI CTCAE v4.0 criteria.

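### Table 7.1-5 asks for adverse events only up to 30 days after study drug discontinuation, while Sections 8.1.1 and 8.2.1 require 100 days

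*Combined protocol and SAP*

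**What the plan says.** Four places in the current text bear on how long adverse events are collected after treatment.

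- Table 7.1-5 (follow-up assessments), note to the adverse event row: "NSAEs and SAEs must be collected up to 30 days after study drug discontinuation". The note then keeps SAEs tied to a later protocol procedure and adds that "SAEs should be reported through the MCRN protocol outlined in Section 8.1".
- Section 8.1.1: "All SAEs must be collected that occur during the screening period and within 100 days of discontinuation of dosing". Beyond that, "The investigator must report any SAE that occurs after these time periods and that is believed to be related" to the study or to a protocol procedure.
- Section 8.2.1: all nonserious events, related or not, are collected during treatment and "for a minimum of 100 days following the last dose of study treatment".
- Section 4.6: "Participants must be followed for at least 100 days after the last dose of study therapy".

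The same row of Table 7.1-5 marks adverse event assessment at Follow-Up Visits 1 and 2 and at the survival visits. Section 9.5.3 states that "All on-study AEs, drug-related AEs, SAEs and drug-related SAEs will be tabulated using worst grade", and it sets no number of days for the on-study period.

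**The concern.** For the same events, the visit table and the adverse event section give different end dates, and the protocol has no rule of precedence. Table 7.1-5 is the schedule a site will have open at follow-up visits. The lead site and up to five others could therefore work to different limits without noticing.

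What is at stake is the completeness of the late safety data. Section 1.4 presents those data as a basis for designing later randomised trials. Because Section 9.5.3 does not say how long the on-study period lasts, the analysis cannot correct for uneven collection.

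**Working it through.** The plan gives no calculated figure to reproduce. The check is a comparison of windows and visit days.

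**Inputs**

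| Source | Events | Window | Counted from |
|---|---|---|---|
| Table 7.1-5 note | nonserious and serious | up to 30 days | study drug discontinuation |
| 8.1.1 | serious | 100 days | discontinuation of dosing |
| 8.2.1 | nonserious | at least 100 days | last dose |
| 4.6 | general follow-up | at least 100 days | last dose |

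**Step 1: gap from a common date.** 100 − 30 = 70 days. For nonserious events 8.2.1 sets a minimum, so 70 is not a strict ceiling.

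**Step 2: gap when the dates differ.** Let D be the days from last dose to the recorded date of discontinuation. Measured from the last dose, the note's limit is D + 30, so the nonserious gap is 100 − (D + 30) = 70 − D.

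- D = 0: 70 days.
- D = 21 (discontinuation dated at the next 3-week dose): 49 days.
- D = 28 (dated at the next 4-week dose): 42 days.
- D = 42 (the 6-week delay limit in 6.5.3.3): 28 days. Section 6.5.3.4 allows longer interruptions in some cases, and these would shrink the gap further.

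For SAEs the gap is 70 days if the two discontinuation phrases mean the same date. It is 70 − D if discontinuation of dosing means the last dose. The documents define neither.

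**Step 3: the note against its own row.** Footnote A to Table 7.1-5 puts Follow-Up 1 at 35 ± 7 days after last dose, which is day 28 to 42. Follow-Up 2 is 80 ± 7 days later: 28 + 73 = 101 to 42 + 87 = 129. Follow-Up 2 therefore falls on days 101 to 129 after last dose. With D = 0 this is 71 to 99 days after the note's limit. With D = 42 the limit is day 72, and Follow-Up 2 is 29 to 57 days after it. The schedule fits a 100-day window and does not fit a 30-day one.

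**Step 4: possible contact with the 13-week toxicity endpoint.** Assume a Monday start of radiotherapy (day 1), last fraction on day 12, first drug dose 14 to 21 days later (day 26 to 33), doses every 21 days, and D = 0. The note's window then closes as follows:

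- after one dose: 26 + 30 = 56 to 33 + 30 = 63;
- after two doses: 47 + 30 = 77 to 54 + 30 = 84;
- after three doses: 68 + 30 = 98 to 75 + 30 = 105.

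Thirteen weeks from the start of radiotherapy is day 91, so only patients who stop after one or two doses are affected. Section 4.1 also describes the period as following the start of the drug combination. On that count it ends at 26 + 91 = 117 to 33 + 91 = 124, and stopping after three doses is included too. Either way, the exposure is to patients who stop early and have not already had a qualifying event.

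**The case against.** The case for leaving this alone has weight. Sections 4.6, 8.1.1 and 8.2.1 all use 100 days, and the visits are spaced to match. The note sets what must be collected and does not forbid collecting more, so a site that follows Section 8 satisfies both texts. The note also sends the reader to Section 8.1 for SAE reporting.

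Several backstops remain. Section 8.1.1 keeps later related SAEs reportable. Section 8.2.1 requires follow-up of nonserious events that led to interruption or discontinuation, or that are present at the end of treatment. Section 7.4.1 asks for every effort to collect toxicity data from all participants, including those withdrawn from treatment. The 13-week endpoint has its own stated period in 4.1, 9.1 and 9.4.1. The safety analysis is descriptive and single-arm.

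Most of this stands, and it sets the size of the problem. It does not remove the contradiction. The pointer to Section 8.1 concerns how SAEs are reported, not how long they are collected, and the note has no pointer to 8.2.1. The backstops leave uncovered new-onset nonserious events and unrelated SAEs after the note's limit. The note's exception for later SAEs is also narrower than 8.1.1, because it covers only those tied to a protocol procedure.

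**Conclusion.** The conflict is real and sits in current operative text. The windows differ by 70 days from a common date, and by 70 − D for nonserious events when discontinuation is dated D days after the last dose (28 days at D = 42). The likely loss is new-onset nonserious events and unrelated SAEs after day 30, which could lower the late counts in the 9.5.3 tables. PFS and OS are unaffected. It is a modest point, but worth correcting.

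Four stronger readings are not supported:

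- **A flat 70-day loss for every patient.** A reader might infer this, but it needs discontinuation, discontinuation of dosing and last dose to be one date, which the documents do not say.
- **Follow-Up 2 always at least 36 days past the note's limit.** This relies on the alternative in 4.6 that places Follow-Up 1 as "coinciding with the date of discontinuation (+/- 7 days) if the date of discontinuation is greater than 35 days after the last dose". Section 4.2.1 and footnote A to Table 7.1-5 count Follow-Up 1 from the last dose only, and Step 3 then gives 29 days at D = 42.
- **A compromised 13-week endpoint.** The contact is limited to early stoppers, and the endpoint has its own observation period.
- **Sites actually recording differently.** This is a reasonable inference from two limits and several sites, but nothing in the documents shows it happening.

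**What to change.** Reconcile the first sentence of the Table 7.1-5 note with 8.1.1 and 8.2.1:

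1. Replace the 30 days with the 100-day window.
2. Name one starting date, for example the last dose, and use it in the note, 8.1.1 and 8.2.1. Changing the number alone would leave the dating ambiguity of Step 2.
3. Refer to 8.1.1 for later related SAEs, so that the note is no longer narrower than that section.
4. In 9.5.3, state that on-study events are those within the same window.

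The cost is a few lines of text and no new visit. If the last dose is the starting date, Follow-Up 2 falls at day 101 at the earliest under footnote A and so covers the whole window. If the date of discontinuation is chosen, the window can run past Follow-Up 2; at D = 42 it ends on day 142 after the last dose. The first survival visit, where the row already marks adverse event assessment, would then cover the remainder. Taking 3 months as about 91 days, that visit comes no earlier than about day 101 + 91 − 14 = 178 after the last dose.

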### 7.1.1 Retesting During Screening

Retesting of laboratory parameters and/or other assessments within the screening period will be permitted (in addition to any parameters that require a confirmatory value). Any new result will override the previous result (i.e., the most current result prior to initiation of thoracic radiation therapy) and is the value by which study inclusion will be assessed, as it represents the participant's most current, clinical state. Laboratory parameters and/or assessments that are included in Table 7.1-1, Screening Procedural Outline may be repeated in an effort to find all possible well-qualified participants. Consultation with the Principal Investigator may be needed to identify whether repeat testing of any particular parameter is clinically relevant.

## 7.2 Study Materials

The following materials will be provided to the site.

- Nivolumab Investigator Brochure
- Ipilimumab Investigator Brochure
- Pharmacy Binder
- Laboratory manuals for collection and handling of blood (including biomarker and immunogenicity) and tissue specimens
- Imaging and Radiation Planning Manual for image acquisition and submission to central vendor
- Pregnancy Surveillance Forms

## 7.3 Safety Assessments

Safety assessments include AEs, physical examinations, vital signs, ECOG performance status, assessment of signs and symptoms, laboratory tests, pregnancy tests as outlined in Section 7.1.

Some of the previously referred to assessments may not be captured as data in the eCRF. They are intended to be used as safety monitoring by the treating physician. Additional testing or assessments may be performed as clinically necessary or where required by institutional or local regulations.

### 7.3.1 Imaging Assessment for the Study

Any incidental findings of potential clinical relevance that are not directly associated with the objectives of the protocol should be evaluated and handled by the investigator as per standard medical/clinical judgment.

## 7.4 Efficacy Assessments

Study evaluations will take place in accordance with the flow charts in Section 7.1. Contrast-enhanced computed tomography (CT) of the chest and CT or magnetic resonance imaging (MRI) of abdomen and any other known or suspected sites of disease are the preferred methods of radiographic assessment of tumors. Repeat CT/MRI of pelvis is required for participants with pelvic metastases at baseline, or if clinically indicated. Brain MRI scan is the preferred imaging method for evaluating CNS metastasis, and assessment is required at screening and every 12 weeks while on study; however, CT of the brain is acceptable if MRI is contraindicated. Patients with incidental asymptomatic brain metastases findings at screening will need to undergo radiation treatment in order to be eligible. Patients are only eligible if according to the clinical judgment of the investigator the finding of an incidental brain metastasis is unlikely to represent progression of disease. The investigator should take results from brain scans at the initial diagnosis into consideration. If a patient has a known allergy to contrast material, please use local prophylaxis standards to obtain the assessment with contrast if at all possible, or use the alternate modality. In cases where contrast is strictly contraindicated, a non-contrast scan will suffice.

All known or suspected sites of disease (including CNS) should be assessed at screening and at subsequent assessments using the same imaging method and technique. If more than one method is used at screening, then the most accurate method according to RECIST 1.1 should be used when recording data and should again be used for all subsequent assessments. Bone scan, PET scan, and ultrasound are not adequate for assessment of RECIST 1.1 response. In selected circumstances where such modalities are the sole modality used to assess certain non-target organs, those non-target organs may be evaluated less frequently. For example, bone scans may need to be repeated only when complete response is identified in target disease or when progression in bone is suspected. Previously treated CNS metastases are not considered measurable lesions for purposes of RECIST 1.1 response. Screening assessments should be performed within 28 days of initiation of radiation therapy. Participants will be evaluated for tumor response outlined in Table 7.4-1 and Table 7.4-2 or more frequently as clinically indicated or per local Standard of Care, until disease progression (or until

discontinuation of study drug in participants receiving study therapy beyond progression), lost to follow-up, withdrawal of study consent, or the study ends. Tumor assessments for all participants should continue as per protocol even if dosing is delayed. Tumor measurements should be made by the same investigator or radiologist for each assessment whenever possible.

As outlined in section 9.4.1, progression free survival will be calculated from the date of patient registration. The baseline scan for RECIST 1.1 response evaluation will be the imaging assessment performed 2 weeks after completion of thoracic radiation and prior to C1D1 of combined ipilimumab/nivolumab. If the patient progresses between pre-treatment imaging and the baseline scan prior to initiation of ipilimumab/nivolumab, this will be considered disease progression according to the defined primary endpoint. In this circumstance, at the investigator's discretion, the patient may elect to receive study drugs beyond progression according to section 6.5.5. Tumor imaging assessments for ongoing study treatment decisions will be completed by the investigator using RECIST 1.1 criteria.

**Table 7.4-1.** Schedule of CT/MRI Tumor Assessments A

Time On Study	Assessment Frequency	Assessment Week (Day 1 of Week Shown)	Assessment Window
Screening		Week 0	± 28 days
Baseline (RECIST 1.1)		Week 4 (prior to initiation of ipilimumab/nivolumab)	+/- 5 days
Between Week 10 and Week 35	Every 8-9 weeks after initiation of Nivolumab/Ipilimumab	10,19,27,35,	± 5 days
Beyond Week 35	Every 12 weeks	47,59,71+,	± 5 days

A-Acceptable Radiographic Tumor Assessments:

---CT/ Chest-With IV contrast preferred.

---CT/MRI Abdomen-With oral and IV contrast preferred.

---CT/MRI Pelvis-With oral and IV contrast preferred. Only required if patient has known pelvic visceral metastases or bony metastases in the pelvis.

**Table 7.4-2.** Schedule of MRI/CT Brain Surveillance Assessments A

Time On Study	Assessment Frequency	Assessment Week (Day 1 of Week Shown)	Assessment Window
Screening/Baseline		Week 0	Within 28 days
Week 10	Every 12-13	Weeks 10, 23, 35, 47,59+	±5 days

	weeks	
--	-------	--

A-MRI/CT Brain-with contrast if possible. MRI preferred.

### 7.4.1 Primary and Secondary Efficacy Assessments

The primary endpoint is progression-free survival at 6 months in all participants. The secondary endpoint is overall survival at 1 year.

See Section 9.4 for the definitions of unacceptable toxicity, OS and PFS. Every effort will be made to collect toxicity, survival and imaging data on all participants, including those withdrawn from treatment for any reason, who are eligible to participate in the study and who have not withdrawn consent for additional data collection. If the death of a participant is not reported, all dates in this study representing a date of participant contact will be used in determination of last known date alive.

## 7.5 Biomarker Assessments

A variety of factors that could potentially predict clinical response to nivolumab and ipilimumab will be investigated in tumor specimens obtained at screening and in peripheral blood taken both at screening (prior to initiation of thoracic radiation therapy) and during the study, from all participants as outlined in Table 7.5-1. The de-identified samples will be sent to DiaCarta which is a company that will be performing DNA and RNA sequencing analysis of the peripheral blood specimens we collected for the trial. The de-identified samples will also be sent to Circulogene which is a company that will be performing DNA and RNA sequencing analysis of the peripheral blood specimens we collected for the trial.

**Table 7.5-1. Biomarker Sampling Schedule for all Participants (MCC 18914)**

Collection Timing A	Serum	PBMC	Tumor	Whole Blood
Study Day	Soluble Biomarkers	Immunophenotyping	Tumor Biopsy	SNP
Screening			X B	
Prior to First Fraction of Thoracic Radiation (0-3 days prior)	X	X		X
After Last Fraction of Thoracic Radiation (0-3 days after)	X	X		
Prior to each dose of ipilimumab/nivolumab or nivolumab therapy	X	X		

Upon Progression	X	X		
At first Follow-Up after study discontinuation	X	X		

ABiomarker sampling occurs prior to dosing and can occur up to 4 days prior to dosing. However, if a sample is collected and the dose is subsequently delayed an additional sample should not be collected.

BSubmission of a tumor sample prior to study initiation is optional.

